4.0 Subject Selection and Withdrawal

4.1 General Characteristics of the Proposed Subject Population

The subject population will be screened from males with low to intermediate risk prostate cancer Gleason score $\leq 7(4+3)$ with PSA below 15 ng/mL who are consented for prostate low dose rate brachytherapy. They will qualify for the study if the planning MRI used for screening and brachytherapy source planning shows at least one region within the prostate that is reported as probable for malignancy by a Diagnostic Radiologist. Treatment planning will be performed per routine, and thus this trial is deemed non-therapeutic as it will not alter treatment. The patient's Urologist will consent them if desired for this study, and will perform the biopsies in the OR prior to proceeding with the prostate brachytherapy procedure as routinely performed with Radiation Oncology and the biopsy locations will be tracked with virtual fiducial markers using the Uronav system in addition to gold fiducial markers. The cost for the additional histopathology will be covered by the study along with required supplies.

The goal for this pilot study is to show feasibility to track histopathology location correlated to standard and functional MR imaging with the possible implication to translate to a therapeutic trial design in subsequent studies to use the combined histopathology data and imaging correlation to direct radiotherapy using either brachytherapy or other forms of radiotherapy such as intensity modulated photon or proton therapy. Post-operative dosimetry will be reported for the whole gland as well as the targeted lesions per routine. The standard goal is to provide 150% of prescribed dose to the region defined as high probability for containing tumor at the time of the brachytherapy implant. As many patients do undergo a combination of both external beam radiation and brachytherapy as a boost dose, the implications could yield a secondary therapeutic trial in higher risk patients where the brachytherapy implant could be completed prior to the external beam therapy, and image guided intensity modulated radiotherapy (IMRT) could be designed to paint dose on the prostate gland following the implant to optimize target coverage. For example if the histopathology confirms cancer, but the post operative dosimetry defines a region that was not fully escalated to 150% of prescribed dose, one can envision using dose painting to target further dose to that region, or conversely if the implant post operative dosimetry shows high doses near any organ at risk such as the rectum or bladder, this area could be dose de-escalated in the additional 25 routine fractions of IMRT.

4.2 Anticipated Number of Research Subjects

The pilot study is designed to include only 6 subjects for testing of feasibility to obtain transperineal tissues and report correlation to MRI image findings.

4.3 Inclusion Criteria

Each of the criteria in the checklist that follows must be met in order for a patient to be considered eligible for this study. Use the checklist to confirm a patient's eligibility. The checklist must be completed for each patient and must be signed and dated by the treating physician.

Patient's Name _____

Medical Record # _____

Research Nurse /
Study Coordinator Signature: _____ Date _____

Enrolling Physician [Print] _____

Enrolling Physician Signature: _____ Date _____

Patients must meet all of the following inclusion criteria to be eligible for enrollment:

_____ 4.3.1 Patients must have histopathology confirmed prostate cancer that is Gleason score $\leq 7(4+3)$ clinical stage $\leq T2aN0M0$ with a PSA below 15 ng/mL.

_____ 4.3.2 Patients must have MRI findings reporting intraprostatic lesions suspicious for malignancy.

_____ 4.3.3 Patient must not have had any prior treatment for prostate cancer

_____ 4.3.4 Age ≥ 18 years.
Because no dosing or adverse event data are currently available on the use of *Uronav* in patients < 18 years of age, children are excluded from this study.

_____ 4.3.5 ECOG Performance status ≤ 2 [See Appendix A].

_____ 4.3.6 Subjects must have an International Prostate Symptom Score of ≤ 15 .

_____ 4.3.7 Subjects must have the ability to understand and the willingness to sign a written informed consent document.

4.4 Exclusion Criteria

The presence of any of the following will exclude a patient from study enrollment.

_____ 4.4.1 Gleason score of $\geq 8(4+4)$

_____ 4.4.2 PSA ≥ 15 ng/mL.

_____ 4.4.3 Clinical stage $> T2b$ or evidence of nodal

_____ 4.4.4 Patients who are on anticoagulants or high dose aspirin therapy that cannot be safely stopped for greater than 10 days prior to treatment should be excluded to limit

increased risk for urinary obstruction.

_____ 4.4.5 Patients with uncontrolled intercurrent illness including, but not limited to ongoing or active infection, symptomatic congestive heart failure, unstable angina pectoris, cardiac arrhythmia, or psychiatric illness/social situations that would limit compliance with study requirements.

_____ 4.4.6 HIV-positive patients on combination antiretroviral therapy are ineligible because of the unlikely risk of prostate cancer being life threatening in this population.

4.5 Subject Recruitment and Screening

Subject will be screened from the practice of the Principle Investigator in men who have consented for prostate brachytherapy.

4.6 Inclusion of Women and Minorities

Women are excluded from participating in this study. Men of all races and ethnic groups are eligible for this trial.

5.0 Registration

All subjects who have been consented are to be registered in the OnCore Database. For those subjects who are consented, but not enrolled, the reason for exclusion must be recorded.

All subjects will be registered through University Hospitals Cleveland Medical Center and will be provided a study number by calling the study coordinator listed on the front page.

5.1 Early Withdrawal of Subjects

5.1.1 Criteria for Removal from Study

Subjects may withdraw from the study at anytime prior to the procedure. They will be replaced by an additional subject to maintain 6 subjects in the cohort.

5.1.2 Follow-up for Withdrawn Subjects

Subjects who withdraw from the study will be followed per departmental routine policy if they proceed with the prostate brachytherapy or elect external beam radiation. They may otherwise elect to be followed by their urologist. As noted above, subject may be replaced to maintain adequate cohort numbers to complete the study.

6.0 Study Biopsy Procedures

6.1 Description biopsy procedure

All biopsies will be completed in the outpatient setting in the ambulatory OR prior to routine prostate brachytherapy under general anesthesia. Patients will be prepped in a dorsal lithotomy position with insertion of a Foley catheter. The perineum will be shaved as needed, and cleansed with antiseptic solution, and the scrotum will be elevated with a towel roll to expose the perineum. The FDA approved DynaCAD and Uronav system will be used to localize the diagnostic MRI findings within the prostate. The 510K approved tranperineal Uronav system will

be used to perform transperineal biopsy with electromagnetic alignment of the transrectal probe and stepper system attached to the perineal biopsy guide 17 gauge template.

Specimens will be sent to anatomic pathology office of:
[name] in separate cassettes at [name]
[name]
[name]

They will be received by [name], PhD.

Each specimen will be sent separately and identified by location in the prostate (1-12 a or p to identify the involved portion of the gland divided in 12 sextants and either anterior or posterior to midline of the coronal plane) along with PIRADS classification of the lesion in MRI report. The proximal and distal end of the sample will be dyed for orientation in the OR at the time of acquisition of each sample, or at a minimum noted if it is from the proximal, mid or distal 1/3 portion of the biopsy cavity to correlate with the same region of the virtual fiducial marker placed at the site of the biopsy.

Standard stains will be used to identify tumors within the specimen with photos taken after processing is completed to allow localization relative to the virtual fiducial marker placed at the site of the biopsy using the Uronav system. The pathology evaluation will be provided through [name].

Biopsy samples will be obtained by hand using direct visualization of the live transrectal ultrasound image with fusion to the mapping MRI obtained preoperatively. The Urologist and Radiation Oncologist will obtain the tissue samples using either an 18 gauge biopsy gun with a 25 cm needle, or additionally may use a FDA approved 17 gauge needle as a trocar to be placed across the perineum and allow for readjustment between biopsies to reduce the number of needle placements and acquire additional biopsy samples using this trocar to reposition the tip to the desired biopsy location (note this step is per part of a pending patent application applied for by UH and the managing PI). The preoperative MRI images obtained prior to the procedure will be reviewed by the investigators, including Radiology, Urology, and Radiation Oncology, to determine the target volume for biopsy using the DynaCAD system, with transfer of the DICOM RT dataset and images to the Uronav system for image guided biopsy. The Uronav and its associated electromagnetic guidance system will be positioned adjacent to the patient in the operating room while the patient is in a dorsal lithotomy position under general anesthesia. The stepper/stabilizing device associated with the Uronav system will be attached to the B&K Flexfocus ultrasound unit after placing the biplanar transrectal probe into position to visualize the prostate gland. Calibration of the encoders on the stabilization unit with the electromagnetic guidance system will be commissioned and maintained by Radiation Physics.

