3.2 Primary Study Endpoints

The primary endpoint will be to report correlation of biopsy tissue histopathology with intraprostatic MRI findings. A total of 12 to 15 tissue samples will be obtained from each subject using standard sextant biopsies in addition to targeted biopsies of intraprostatic MRI findings. Assuming 14 specimens are sent for histopathology analysis in 6 subjects we will use the 84 biopsy sites to report sensitivity and specificity for the MRI findings along with positive and negative predictive values.

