3.3 Secondary Study Endpoints

3.3.1 We will report the post-operative radiation dose coverage for the prostate, organs at risk, and targeted lesion for each case. The coverage for the brachytherapy implant will be reported for the V100, V150, and V200, i.e. volumes of the prostate receiving 100, 150, and 200% of the prescribed dose. The dose delivered to the targeted lesion or lesions will be reported as a V100, V150, V200 as well to evaluate the ability to target the dose escalation prospectively, though again is per routine and not as part of a therapeutic trial design at this time. Additionally, the D90, i.e. dose to 90 percent of the prostate volume will be reported. Doses to the bladder, rectum and urethra will also be calculated for evaluation in the study.

3.3.2 An additional secondary endpoint for the study will be to report the incidence of successful completion of the transperineal biopsy procedure using the Uronav system which is provided by Philips Medical as part of the support for this study. The Symphony biopsy system will be available in the operating room (OR) as a back-up to complete the biopsies if needed. It is, however, anticipated that the combined DynaCAD computer for processing the MR images and Uronav systems supplied for the study to integrate with our standard transperineal ultrasound system will be 100% successful in obtaining the required biopsies. We will also report on any unanticipated complications or infections. It is anticipated that the risk of infection should be substantially diminished by avoiding transrectal biopsies. However, the risk for prostate edema and urinary obstruction may be increased due to the additional transperineal needle placement as the biopsy will be followed by routine prostate brachytherapy. Patients may therefore be asked to maintain a Foley catheter overnight to allow edema to resolve, and avoid acute obstruction the following day. Assuming the Uronav system is capable of completing biopsies on all patients and no more than 1 patient acquires a post-operative infection this pilot study will be deemed a success, and further investigation may be warranted.

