9.2 Effectiveness Assessments

Effectiveness will be analyzed by the rate of urinary obstruction beyond 7 days or infection directly related to the procedure, in addition to the analysis for the correlation of the biopsy samples with preoperative MR imaging. Statistical analysis of effectiveness is not anticipated due to the limited number of subjects in this exploratory initial analysis.

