10.0 Statistical Plan

10.1 Sample Size Determination

Sample size justification: This is a hypothesis-generating pilot study with enrollment of 6 patients. Each patient is expected to have 12 to 15 tissue samples using standard sextant biopsies in addition to targeted biopsies of intraprostatic MRI findings. Assuming 14 specimens are sent for histopathology analysis in 6 subjects we will use the 84 biopsy sites. Based on the report in the literature [6], we expect the cancer lesion detection rate of 22% using multiparametric MRI/US fusion vs. 11% under current standard care. Ignoring the potential correlation of multiple lesions from the same patient, 6 patients (84 lesions) will have 82% power to detect in 11% improvement of detection rate using 2-sided one-sample chi-square test with a significance level of 0.05.

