10.2 Statistical Methods

Statistical analysis: The correlation of biopsy tissue histopathology with intraprostatic MRI findings will be estimated using binomial evaluation for True Positive, False Positive, True Negative, False Negative values to report Sensitivity, Specificity, and Positive as well as Negative Predictive value for parametric MRI findings relative to correlated histopathology. These data will be used for reporting the study results in regards to Specific aim 1, The infection rate and hospitalization rate within 30 days due to the procedure will be collected for expected acute events (AE's) and these data will be used for reporting the study results for specific aim 2 evaluation the transperineal use of Uronav to determine if the transperineal biopsy approach results in a reduced rate of infection or hospitalization compared to standard transrectal biopsies.

Any deviations from the previously described statistical plan will be described and justified in a protocol amendment.

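### Each specimen goes to pathology with its PI-RADS class, so the reference histology for the primary MRI accuracy statistics can be read knowing the MRI result

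*Combined protocol and SAP*

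**What the plan says.** Section 6.1 describes what accompanies each core. Specimens go separately, coded by location (1-12, anterior or posterior), "along with PIRADS classification of the lesion in MRI report". Each core is also dyed or annotated for orientation so that it can be matched to a virtual fiducial marker. The section says who receives the specimens and, in a separate sentence, that "The pathology evaluation will be provided through" a named source; both names are removed from the public text. It sets no condition on what the reader may know.

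Section 3.2 states that "The primary endpoint will be to report correlation of biopsy tissue histopathology with intraprostatic MRI findings". The cores are taken "using standard sextant biopsies in addition to targeted biopsies of intraprostatic MRI findings". Section 10.2 sets out the analysis: classify results as true or false positive or negative, then "to report Sensitivity, Specificity, and Positive as well as Negative Predictive value for parametric MRI findings relative to correlated histopathology". Histology is therefore the reference standard and MRI the index test.

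**The concern.** In an accuracy study the reference should be read without knowledge of the index test. Otherwise an equivocal focus may be called cancer because the MRI was suspicious, or benign because it was not. Either tendency turns discordant cores into concordant ones and raises all four accuracy statistics together.

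Here the protocol does more than leave masking unmentioned: it instructs that the MRI class travel with the tissue. The class belongs to a lesion, so sextant cores outside any lesion may carry none. In that case its mere presence or absence would show which cores were targeted.

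Accuracy is the named primary endpoint, and section 4.1 looks ahead to a possible therapeutic trial using the imaging-histology correlation. Enrolling more patients would not remove a bias of this kind, and cores already read with the class known could be masked afterwards only by a re-read.

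**Working it through.** **What the text supports**

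1. The index result accompanies the specimen (6.1).
2. Histology is the reference for the primary statistics (3.2, 10.2).
3. No section masks the reader, delays release of the class until the read is final, or plans a second masked read. The background (1.2) uses the word blind, but of ultrasound-guided biopsy. Sections 2.0, 4.1, 6.1 and 9.3 cover the MRI call, target selection and the comparison with histology, and none addresses the reader.
4. The documents do not show that the class reaches the reader. Receipt and evaluation are described separately, with names removed.

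So exposure is possible under the written procedure but not demonstrated.

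**Plan's own figures**

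The number of cores is 6 × 14 = 84 (3.2, 10.1). The 82% power in 10.1 reproduces approximately: Φ[(0.22 − 0.11 − 1.96 × √(0.11 × 0.89/84)) / √(0.22 × 0.78/84)] = 0.830. It has no bearing on this point, and the plan gives no figure for reader bias.

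**Illustration of size**

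Only the 84 comes from the plan. Assume 18 MRI-positive cores with PPV 0.5, and cancer in 10% of the 66 MRI-negative cores. Then TP = 9, FP = 9, FN = 6.6 and TN = 59.4. Let a fraction f of discordant cores be misread towards the MRI result, so that f × FP moves to TP and f × FN moves to TN. The upward direction is built into this assumption.

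- f = 0.10 moves 0.9 + 0.66 = 1.56 cores: TP 9.9, FP 8.1, FN 5.94, TN 60.06.
- f = 0.20 moves 3.12 cores: TP 10.8, FP 7.2, FN 5.28, TN 60.72.

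The half-width is 1.96 × √(p(1−p)/n) at f = 0, ignoring clustering.

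| Statistic | f = 0 | f = 0.10 | f = 0.20 | n | 95% half-width |
|---|---|---|---|---|---|
| Sensitivity, TP/(TP+FN) | 0.577 | 0.625 | 0.672 | 15.6 | 0.245 |
| Specificity, TN/(TN+FP) | 0.868 | 0.881 | 0.894 | 68.4 | 0.080 |
| PPV, TP/(TP+FP) | 0.500 | 0.550 | 0.600 | 18 | 0.231 |
| NPV, TN/(TN+FN) | 0.900 | 0.910 | 0.920 | 66 | 0.072 |

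**Range over 27 assumed scenarios** (MRI-positive cores 12, 18 or 24; PPV 0.3, 0.5 or 0.7; cancer in MRI-negative cores 0.05, 0.10 or 0.15)

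| Statistic | Shift at f = 0.10 | Shift at f = 0.20 | Largest shift ÷ half-width at f = 0.20 |
|---|---|---|---|
| Sensitivity | 0.018–0.079 | 0.035–0.150 | 0.150/0.242 = 0.62 |
| PPV | 0.030–0.070 | 0.060–0.140 | 0.140/0.183 = 0.76 |
| Specificity | 0.005–0.022 | 0.010–0.045 | 0.0449/0.1028 = 0.44 |
| NPV | 0.005–0.015 | 0.010–0.030 | 0.030/0.0825 = 0.36 |

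Every shift stays below the unclustered half-width. Correlation between cores from the same patient would generally widen the intervals further.

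**Other assumed cells**

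Take 12 MRI-positive cores (6 cancer, 6 benign) and 72 MRI-negative cores (8 cancer, 64 benign). Sensitivity goes from 0.429 to 0.438, 0.453 and 0.478 at f = 0.02, 0.05 and 0.10, and PPV from 0.500 to 0.510, 0.525 and 0.550. The direction is the same by construction, and at 2–5% the shifts are small.

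**The case against.** The strongest reply is that exposure is not shown. The person who receives the specimens may not read the slides, and a laboratory step may keep the class from the reader. That stands, and the claim is limited accordingly: histology can be read knowing the MRI result. If such a step exists, one sentence in 6.1 would settle the matter.

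Second, the class may add little. Sections 4.3.1 and 4.3.2 mean every subject has confirmed cancer and a suspicious lesion, and location must accompany each core for mapping. This partly stands: masking would be incomplete. The class is nevertheless the most direct cue, and the mapping does not need it.

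Third, linking lesion class to tissue is the purpose of the study (4.1, 9.3). So it is, but a specimen number achieves that linkage after the read.

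Fourth, the MRI call and targets are fixed before biopsy (4.1, 6.1, 7.0), so influence cannot run the other way, and calling tumour on standard stains may leave little room for suggestion. The first part is correct. The second is plausible: any effect is probably confined mainly to small or equivocal foci, though the documents do not quantify it.

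Finally, the misread fractions have no support in the documents. That is so. The figures show direction and rough scale under stated assumptions; they are not an estimate.

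**Conclusion.** The concern holds as a minor design weakness, with medium confidence. The written procedure opens the reference read to the index result and contains no safeguard. The conclusion rests on the text of 6.1, 3.2 and 10.2; the direction of bias further assumes that the reader sees the class and is swayed by it. The size is unknown, and in every scenario tried, up to 20% of discordant cores misread, it is smaller than sampling error.

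The consequences are limited. Section 10.1 says "This is a hypothesis-generating pilot study with enrollment of 6 patients". Under 3.3.2, if biopsies are completed in all patients and "no more than 1 patient acquires a post-operative infection this pilot study will be deemed a success", accuracy plays no part in that judgement. Section 9.2 adds that "Statistical analysis of effectiveness is not anticipated due to the limited number of subjects", and 9.3 rules out treatment changes based on the results. The case for acting is that accuracy is still the primary endpoint and the safeguard costs little.

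**What to change.** In 6.1, remove the PI-RADS class from the specimen label and requisition, together with any marker that distinguishes targeted from systematic cores if the forms carry one. Give each core a unique sequential number alongside its location code and orientation dye or note. The number is needed because a sextant core and a targeted core from the same subject can share a location code. Record PI-RADS and target status against that number on the case report form in OnCore, and link them only after the histology result has been recorded.

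In 10.2, state that histology was read without the PI-RADS class and that masking was partial because location was visible. If the laboratory already withholds the class, describe that arrangement instead.

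The cost is one number per core (12 to 15 per subject, about 84 in all), a revised label and requisition, one form field and one sentence in 10.2. There is no added procedure for the subject. The downsides are that the pathologist lacks imaging context at the time of reading, and that location, or a second core from the same location, may still suggest a target.

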7.0 Study Procedures

Study Procedures	Screening (within 60 days of biopsy)	Biopsy	Visit 3 ~2 weeks Post	Visit 4 1 month Post	Visit 5 3 months Post
Informed consent	X				
Demographics	X				
Medical History	X			X	X
Height and Weight	X			X	X
Vitals ¹	X			X	X
Concomitant Med Assessment	X			X	X
ECOG Status	X		X	X	X
Adverse events assessment	X	X	X	X	X
Uronav Guided Biopsy		X			
Pathology		X			

1. Including blood pressure and pulse rate

